### 3.3 Interventions

#### 3.3.1. Experimental group – Skin adhesive

Following fascial closure, the skin edges are approximately with subcutaneous absorbable sutures and the epidermal layer is sealed with 2-octyl cyanoacrylate skin adhesive (Leukosan Adhesive). The adhesive is applied in three thin layers with 30 second drying intervals per manufacturer instructions. No additional wound dressing is applied.

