#### 3.3.2. Control group- conventional skin stapling

Following fascial closure, the subcutaneous layer is sutured by Vicryl and skin is approximately using a disposable skin stapler (Visistat Regular). Staples are placed at approximately 5mm intervals. Standard wound dressings are applied. Staples are removed at the discretion of the attending surgeon, typically a postoperative day 7-10.

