### 3.4 Randomization

Randomization was performed using a computer-generated sequence created by the Department of Biostatistics at Seoul St. Mary's Hospital. Allocation was stratified by surgical approach (laparoscopic vs robotic-assisted) and tumor location (colon vs rectum). Within each stratum, block randomization with variable block sizes (4,6, and 8) ensured balance while minimizing predictability.

Allocation concealment was achieved through a centralized, web-based system managed by an independent biostatistician not involved in patient recruitment, enrollment, or outcomes assessment. Patients were randomized

the day before surgery in a 1:1 ratio to either the skin adhesive (Bond) or skin stapling (Stapler) group. Treatment allocation was concealed from all clinical staff until assignment.

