### **3.5 Blinding**

This was an open-label trial; patients and clinicians were not blinded. However, outcome assessors were blinded to treatment assignment. Physicians performed postoperative wound assessment on the day of discharge, and statistical analyses were conducted without knowledge of group assignment until completion.

The open-label design was necessary due to the visibly distinct nature of the interventions. To minimize potential independent clinical nurse specialists, not involved in surgery or allocation, conducted wound evaluations and patient satisfaction surveys.

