### **3.7. Data Collection**

Baseline variables will be collected preoperatively and include: age, sex, body mass index (BMI), ASA class, diabetes mellitus status, smoking history, prior abdominal surgery, preoperative serum white blood cell count (WBC), and C-reactive protein (CRP). Intraoperative data will include operative technique, type of resection, specimen extraction incision length, operative time, and estimated blood loss. Postoperative data will include histopathological results (tumor type, TNM stage), SSI occurrence, VAS pain scores, length of stay, complications, wound care resource utilization, and patient-reported satisfaction.

All data will be recorded on standardized case report forms (CRFs) and entered into a password-protected electronic database. Source data verification will be performed quarterly by the principle investigator.

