## 4. Study Schedule

		Study Period						
		Enrollment	Allocation	Post-allocation				Close-out
	Time point	-2 to 0 day	Operation day	Postoperative day 1	Postoperative day 2	Postoperative day 3	Discharge	First OPD f/u
Enrollment	Eligibility screen	O						
	Informed consent	O						
	Randomization		O					
	Allocation		O					
Intervention	Experimental intervention		O					
	Control intervention		O					
Assessment	Demographical data	O						
	Medical history	O						
	Laboratory	O	O		O		O	
	Parameters of surgical procedure		O					
	VAS score		O	O	O	O		
	Documentation of SSI		O	O	O	O		O
	Documentation of other complication		O	O	O	O		O
	Length of hospital stay							O
	readmission							O
	Patient questionnaire							O
	Pathologic results							O
	Cost outcomes							O

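### Sections 3.4 and 4 give different days for randomisation, and neither withholds the arm from the operating team until it is needed at closure

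*Protocol*

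**What the plan says.** Protocol section 3.4 states that patients were randomised "the day before surgery in a 1:1 ratio to either the skin adhesive (Bond) or skin stapling (Stapler) group", through a central web-based system run by an independent biostatistician. On disclosure it says: "Treatment allocation was concealed from all clinical staff until assignment". It gives no later point at which the operating team learns the arm.

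The schedule in section 4 has a row "Randomization" whose only mark is in the column "Operation day". The allocation row and both intervention rows are marked in that same column. Eligibility screening and consent are marked one column earlier.

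Section 3.5 states: "This was an open-label trial; patients and clinicians were not blinded". It adds that outcome assessors were blinded.

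The arm-specific procedures begin at the same operative point. For adhesive (section 3.3.1): "Following fascial closure, the skin edges are approximately with subcutaneous absorbable sutures". For stapling (section 3.3.2): "Following fascial closure, the subcutaneous layer is sutured by Vicryl".

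The primary endpoint (section 3.6.1) is superficial or deep incisional SSI within 30 days. Operative time, a secondary endpoint (section 3.6.2), is counted from skin incision to wound closure. Intraoperative data (section 3.7) include "specimen extraction incision length, operative time, and estimated blood loss".

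**The concern.** There are two separate problems.

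The first is a contradiction. A site cannot randomise both on the day before surgery and on the day of surgery. The choice affects who is in the trial. The earlier the assignment, the more patients enter the intention-to-treat set whose operation is then cancelled or changed before any skin closure. Section 3.9 claims non-inferiority only if the intention-to-treat and per-protocol analyses agree, so the make-up of the randomised set matters. Section 3.8 makes no dropout allowance, on the ground that the closures are carried out at surgery. That reasoning fits assignment in theatre better than assignment the day before.

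The second is a design weakness that exists whichever day is meant. The surgeon needs the arm only once the fascia is closed, yet may know it from the moment of assignment. The extraction incision and the handling of the wound up to fascial closure come before the arms diverge and may bear on incisional SSI. If they differ by arm, the comparison no longer isolates the closure method, and neither analysis set corrects for it. Operative time is exposed over its whole length.

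**Working it through.** **Timing, side by side**

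| Item | Section 3.4 | Section 4 |
|---|---|---|
| Randomisation | day before surgery | operation day |
| Allocation | concealed until assignment | operation day |
| Arm withheld until fascial closure | not stated | not stated |

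Damage to the table in reading the PDF is an unlikely explanation. The randomisation mark lines up with the allocation and intervention marks, and the screening and consent marks sit in a different column.

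**Can the operating team know the arm before it is needed?**

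1. Concealment ends at assignment (3.4).
2. Clinicians are unblinded (3.5).
3. The arms first differ after fascial closure (3.3.1, 3.3.2).
4. No section sets a later release.

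So yes under section 3.4. It is also yes under section 4 if the operation-day assignment is made before incision, which the schedule permits.

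**The plan's own sample size, as a check on the inputs.** From section 3.8: SSI rates 0.058 (stapling) and 0.010 (adhesive), margin 0.0099, one-sided alpha 0.025, power 80%, unpooled Z.

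n per arm = (0.058×0.942 + 0.010×0.990) × (1.960 + 0.842)² / (0.0099 + 0.048)² = 0.06454 × 7.849 / 0.003352 = 151.1, rounded up to 152. Power at 152 is 0.8023. This reproduces the stated figures. Changing the time of randomisation does not alter this calculation.

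**How few events decide the result**

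- Expected SSIs at the planning rates: 152 × 0.058 = 8.8 stapling and 152 × 0.010 = 1.5 adhesive.
- One SSI is 1/152 = 0.66 percentage points.
- The margin is 0.0099 × 152 = 1.5 SSIs.
- With 9 stapling and 3 adhesive SSIs, the upper 95% bound is −3.95 + 1.96 × 2.22 = 0.41 points, which passes.
- With 9 and 4, it is −3.29 + 1.96 × 2.31 = 1.24 points, which fails.

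**Illustration under assumed shifts.** The table comes from exact enumeration of both binomial counts under the section 3.9 rule, with 152 per arm and a stapling rate of 5.80%. The starting adhesive rate is the non-inferiority boundary, 5.80 + 0.99 = 6.79%. The shift is an assumed lowering of adhesive-arm risk by arm-aware care before closure.

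| Assumed shift (points) | Adhesive rate | Probability of declaring non-inferiority |
|---|---|---|
| 0 | 6.79% | 2.6% |
| 0.5 | 6.29% | 3.9% |
| 1 | 5.79% | 5.7% |
| 2 | 4.79% | 12.1% |

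The shifts have no source in the documents. A 2-point shift is 2/6.79 = 29% of the risk, a large effect for care before closure alone. A shift against adhesive would lower the probability instead.

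**The case against.** The strongest reply is that a clerical conflict and a design preference are being joined. That is right as far as it goes: the two are independent. A reader might infer that bringing section 3.4 into line with the schedule would cure the exposure. It would not, because the schedule does not place randomisation after fascial closure.

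A reader might also infer that the schedule lets consent follow randomisation, since its enrolment window runs to day 0. The documents do not support this. Section 3.2.1 requires written consent before enrolment, and the window is an outer limit.

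Nor do they support a claim that bias occurred. No section says that incision length or wound handling varies with the closure method. The trial is declared open-label with a reason given, central concealment guards against selection bias, and assessors are stated to be blinded. Incision length, operative time and blood loss are recorded, so arm differences in those items could be examined.

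This stands, but it does not remove the point. The visible difference between closures explains unblinding from skin closure onward, not before it. Blinded assessment addresses detection bias, not care during the operation. Care that is not recorded cannot be compared between arms.

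Two further limits also stand. Late release leaves clinicians unblinded after closure, when dressings differ by arm. And the protocol gives no reason for day-before assignment, so one cannot say that it serves no purpose; logistics may be one.

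**Conclusion.** The contradiction between sections 3.4 and 4 is certain and must be reconciled. Its effect on the intention-to-treat population cannot be sized, because the documents give no rate of cancelled or changed operations.

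The exposure before closure is a real and avoidable weakness, but only a possible bias. It rests on the absence of any rule withholding the arm until fascial closure, and on the assumption that some care before closure both affects the outcome and could vary with knowledge of the arm. The event counts show that a shift of one or two SSIs can reverse the primary conclusion. That sensitivity comes from the small margin and low event rate and is not evidence of bias. A reader might take 3.9%, 5.7% and 12.1% as estimates of the trial's error rate. They are illustrations under assumed shifts in one direction only.

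The change is worth making because it is cheap. The finding does not by itself invalidate the trial.

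**What to change.** 1. State one time of randomisation, identically in sections 3.4 and 4, with eligibility and consent completed before it.
2. Have the existing web system release the arm to the operating team only after fascial closure, immediately before skin closure. Preferably randomise at that point; both stratification factors, surgical approach and tumour location, should be known by then. If the assignment is generated earlier for logistical reasons, keep it hidden in the system until then.
3. Sections 3.4 and 3.5 are in the past tense while other sections use the future, so the documents do not settle whether patients have already been randomised. If they have been, under section 3.4, correct the schedule to describe what was done and apply late release to the remaining patients.

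The cost is wording in two sections and one log-in during each operation. The sample size calculation is unchanged. Bias after closure is not removed.

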### **3.5 Blinding**

This was an open-label trial; patients and clinicians were not blinded. However, outcome assessors were blinded to treatment assignment. Physicians performed postoperative wound assessment on the day of discharge, and statistical analyses were conducted without knowledge of group assignment until completion.

The open-label design was necessary due to the visibly distinct nature of the interventions. To minimize potential independent clinical nurse specialists, not involved in surgery or allocation, conducted wound evaluations and patient satisfaction surveys.

### **3.6. Outcomes**

#### **3.6.1 primary Endpoint**

Incidence of SSI (superficial or deep incisional) within 30 days of surgery.

#### **3.6.2 Secondary Endpoints**

Outcomes	Measurement Tool	Time point
Pain score	Visual Analogue Scale (VAS, 0-10)	POD1, 2, and 3
Length of hospital stay	Day from surgery to discharge	At discharge
Operative time	Minutes (skin incision to wound closure)	Intraoperative
Major complications	Clavien-Dindo classification	Within 30 days
Cost effectiveness	Dressing supply cost, dressing service cost, Dressing frequency	Until discharge
Patient satisfaction and wound quality	Validated wound questionnaire, investigator wound assessment	1 week postop discharge OPD visit

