### 2.2 Secondary objective

To compare postoperative pain intensity (VAS score, 0-10) at postoperative days 1 and 3.

To compare length of hospital stay.

To compare the incidence of major postoperative complications within 30 days

To compare total operative times (minutes).

To compare total wound-related cost-effectiveness between the two groups, including device cost and wound dressing service cost.

To assess wound healing quality and patient satisfaction via a validated questionnaire administered at the outpatient clinic visit one week after discharge.

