### 3.9 Statistical Analysis

All analyses will be performed using SPSS version 27.0 (IBM Corp) or R version 4.3 or later. The primary non-inferiority analysis will be conducted on both the per-protocol (PP) population and the intention-to-treat (ITT) population; non-inferiority will be claimed only if both analyses are concordant.

The primary endpoint (SSI rate) will be analyzed using a one-sided Z test for the difference in proportions, with the 95% confidence interval for the difference (skin adhesive minus stapling) reported. Non-inferiority will be concluded if the upper bound of the 95% confidence interval is below the pre-specified non-inferiority margin of 0.99 percentage points.

Continuous secondary endpoints (VAS, length of stay, operative time, cost) will be compared using the Student's t-test or Mann-Whitney U test as appropriate. Categorical variables (complication rates, patient satisfaction categories, pathological stage) will be analyzed using the chi-square test or Fisher's exact test. A two-tailed p-value of <0.05 will be considered statistically significant for all secondary comparisons.

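### The cost endpoint in 3.6.2 omits the device cost that objective 2.2 includes and stops at discharge, so it mainly reproduces the assigned dressing policy and cannot show the net wound-related cost difference

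*Protocol*

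**What the plan says.** Four parts of the Protocol bear on cost.

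- **Objective (2.2).** The comparison is of "total wound-related cost-effectiveness between the two groups, including device cost and wound dressing service cost". Device and dressing service are named as separate components.
- **Endpoint table (3.6.2).** Under cost effectiveness the measurement is "Dressing supply cost, dressing service cost, Dressing frequency", and the time point is up to discharge. That is two cost items and one count. Neither the adhesive, the stapler nor staple removal is listed.
- **Interventions (3.3.1, 3.3.2).** For the adhesive arm: "No additional wound dressing is applied". The stapling arm receives ordinary dressings, and "Staples are removed at the discretion of the attending surgeon, typically a postoperative day 7-10".
- **Schedule and analysis (4, 3.9).** The row "Cost outcomes" is marked at the first outpatient visit. Cost is listed among the continuous secondary endpoints, to be compared by t-test or Mann-Whitney test as appropriate.

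Section 3.7 adds that wound care resource use will be collected, without itemising it.

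**The concern.** The objective and the endpoint that should answer it do not match. The objective asks about total wound-related cost and names the device. The endpoint counts dressings only. Routine dressing use is also what the protocol assigns differently to the two arms, so a difference on the listed items is expected from the allocation itself and says little about whether the adhesive strategy is cheaper overall.

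The window adds to this. A cost that ends at discharge can miss staple removal, a cost that only the stapling arm bears.

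The Background names cost-effectiveness, alongside infection incidence, as something for which randomised evidence is lacking. If 3.6.2 is followed as written, the trial will report a dressing-cost difference under a cost-effectiveness label and will not have measured what 2.2 set out to measure.

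**Working it through.** The Protocol states no cost figure and no prices, so there is nothing to reproduce and no amount in money can be given. What can be checked is which terms each definition contains and which way each omission acts.

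**Notation, per patient**

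- D: mean routine dressing cost (supplies and service) up to discharge in the stapling arm. It is positive, because 3.3.2 gives that arm dressings.
- Routine dressing cost in the adhesive arm: taken as 0, from 3.3.1.
- A, S: device cost of adhesive and of stapler. Both are named in 2.2 as device cost and both are absent from 3.6.2.
- R: cost of staple removal, borne only by the stapling arm and listed in neither section.
- Dressings prompted by wound complications are set aside here.

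**Difference, adhesive minus stapling**

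1. Endpoint table (3.6.2): 0 - D = -D.
2. Objective (2.2), with device cost: (A + 0) - (S + D) = (A - S) - D.
3. With staple removal as well: (A - S) - D - R.

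Line 1 contains neither A nor S, so no device price can alter it. Line 2 is zero when A - S = D. Line 3 is zero when A - S = D + R.

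**Assumed range, in units of D.** These inputs are assumptions, because the Protocol supplies none: A - S from -0.5 to 2, and R from 0 to 0.5.

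| A - S | R | 3.6.2 as written | With device | With device and removal |
|---|---|---|---|---|
| -0.5 | 0.5 | -1 | -0.5 - 1 = -1.5 | -1.5 - 0.5 = -2.0 |
| 0 | 0.25 | -1 | 0 - 1 = -1 | -1 - 0.25 = -1.25 |
| 1 | 0 | -1 | 1 - 1 = 0 | 0 - 0 = 0 |
| 1.5 | 0.5 | -1 | 1.5 - 1 = 0.5 | 0.5 - 0.5 = 0 |
| 2 | 0 | -1 | 2 - 1 = 1 | 1 - 0 = 1 |

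The table's definition stays at -1 throughout. With device cost the difference runs from -1.5 to +1. With device cost and removal it runs from -2.0 to +1.

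**Direction of each omission**

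- Device: leaving it out flatters adhesive if A > S and penalises it if A < S. The Protocol does not say which holds.
- Staple removal: leaving it out drops R from the stapling arm only, which works against adhesive.

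The two can act in opposite directions, and without prices the net cannot be signed.

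**The case against.** Several points on the other side are sound.

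- **Dressings avoided are a real saving.** Going without a dressing is part of the adhesive strategy, so counting it is legitimate. This stands. The fault is that the count is incomplete, not that dressings are in it.
- **The adhesive arm is not fixed at zero.** The sentence in 3.3.1 describes closure. It does not bar later dressings for dehiscence or infection, both of which 5.1 anticipates. This stands, so only the routine part of the difference is set by the protocol.
- **Device cost is in the Protocol.** It is in 2.2, and the uncategorised resource data in 3.7 might capture it. The first half is true and is why the point is a mismatch between two sections. The second half does not repair 3.6.2, which is where the endpoint is defined.
- **The schedule need not conflict with 3.6.2.** The first-outpatient column also holds length of stay, which 3.6.2 fixes at discharge. The column may show only when data are recorded. This stands, and no contradiction with the schedule is claimed here.
- **The choice of test.** Section 3.9 already permits a comparison of means, and the choice between tests may be left to a statistical analysis plan. The option of a rank test is therefore not a fault in itself.

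A reader might go further and infer that the endpoint favours adhesive by construction. The documents do not support that for net cost. Omitting staple removal points the other way, and the effect of omitting the device depends on prices that are not given.

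**Conclusion.** The concern holds as a mismatch between objective and endpoint. Section 3.6.2 leaves out a component that 2.2 expressly includes, and its window may close before staple removal. What remains mainly reflects which arm was assigned dressings, so the endpoint cannot show the net wound-related cost difference.

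The size cannot be put in money. The conclusion needs only that routine dressing cost is near zero with adhesive and positive with staples, as 3.3.1 and 3.3.2 imply. The range shown in the working is illustrative and serves only to show that the omitted terms can change the sign. No bias in favour of either arm is established.

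The matter is worth correcting because cost is one of the trial's stated reasons, but it concerns one secondary endpoint. The primary non-inferiority conclusion does not depend on it.

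**What to change.** In 3.6.2, define per-patient wound-related cost as:

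closure device cost + dressing supply and service cost + staple-removal cost

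Use one window, the same in both arms and long enough to cover staple removal. The first outpatient visit is a natural choice where removal has taken place by then, since section 4 already records cost there. Dressing frequency can stay as a separate descriptive count. Bring the wording of 2.2 into line.

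In 3.9, report the difference in mean cost with a 95% confidence interval. Call the result a cost comparison unless it is related to infections avoided.

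The price is a few extra case report form or billing fields and a short change of wording. The cost difference shown may move in either direction.

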### **3.7. Data Collection**

Baseline variables will be collected preoperatively and include: age, sex, body mass index (BMI), ASA class, diabetes mellitus status, smoking history, prior abdominal surgery, preoperative serum white blood cell count (WBC), and C-reactive protein (CRP). Intraoperative data will include operative technique, type of resection, specimen extraction incision length, operative time, and estimated blood loss. Postoperative data will include histopathological results (tumor type, TNM stage), SSI occurrence, VAS pain scores, length of stay, complications, wound care resource utilization, and patient-reported satisfaction.

All data will be recorded on standardized case report forms (CRFs) and entered into a password-protected electronic database. Source data verification will be performed quarterly by the principle investigator.

